2.5.3 Other Safety Assessments

Data for vital signs will be summarized by treatment group using descriptive statistics with the value at each visit as well as the change from baseline. The numbers and percentages of subjects with abnormalities in focused physical examination and for the safety assessment of jawline and oral commissures will also be summarized by treatment group. The results of the urine pregnancy tests will only be listed.

[figure not shown]
AEs of special interest (AESIs) for abobotulinumtoxinA are TEAEs that suggest a possible remote spread of effect of the toxin or events suggestive of hypersensitivity like reactions. TEAEs due to possible remote spread of the effects of abobotulinumtoxinA will be identified using the list of MedDRA PTs compatible with the mechanism of action of BoNT-A and based on the recommendations from the Committee for Medicinal Products for Human Use (CHMP) and the FDA. TEAEs potentially representing hypersensitivity reactions will be identified using the Standardised MedDRA Query (SMQ) (narrow search query) for hypersensitivity reactions. A list of adverse events potentially suggestive of remote spread of toxin is in Section 5 Appendix A. A list of MedDRA PTs in the hypersensitivity SMQ is in Section 6 Appendix B.

All TEAEs identified using the search strategy described above will be medically evaluated during the study, before the database lock and unblinding, by the sponsor to identify events which could possibly represent "remote spread of effect of toxin", or which are suggestive of "hypersensitivity reactions" due to study treatment administration. Cases will be excluded if they are confounded by presence of alternative clinical etiologies (medical history, concomitant medication or diagnosis which could account for the symptoms); if they are considered to be local effects instead of distant spread as judged by the site of injection; the time period between study treatment administration and event onset is not in accordance with the expected mechanism of action; or due to insufficient information/evidence to make an assessment.

Doc id 43USD1804 Statistical analysis plan -🖧 GALDERMA

In the tables and listings, only the final list of AESIs confirmed by the sponsor as "a possible remote spread event" or "hypersensitivity reactions" will be taken into account.

Data Safety Monitoring Committee Reviews

Pre-Specified Stopping Criteria 2.6.1

The DSMC reviews will be based on tables of summary statistics and listings. No statistical inference will be performed.

Evaluation of safety data will include application of the following stopping criteria:

Further, the DSMC will review the list of AEs (including confirmed AEs of local or remote spread of toxin) and advise the Sponsor of safety findings that may result in discontinuation of study enrollment. If study enrollment is discontinued, all previously enrolled subjects will continue in the study

[figure not shown]
Interim Analyses

[figure not shown]
An interim analysis is not planned for this study.

2.8 **Determination of Sample Size**

[figure not shown]

3 Reference List

There are no other references beyond those that are included in the protocol.

Doc id

Effective

Effective date: 2019-12-23 06:09

Effective

Version: 1.0

Version: 1.0

Effective

Effective date: 2019-12-23 06:09

Effective

Effective date: 2019-12-23 06:09

Version: 1.0

Effective date: 2019-12-23 06:09

Effective

Version: 1.0

Effective date: 2019-12-23 06:09

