9.1.3.1 Safety Analysis

AEs will be summarized descriptively by treatment group, SOC and PT using number and percentage of subjects with at least one event and number of events. The results will be further broken down by other factors such as severity, causality, seriousness, and whether the event led to discontinuation, and action taken for the event. Duration and time to onset of related AEs will also be presented by treatment group, SOC and PT.

The numbers and percentages of subjects with abnormalities in physical examination will also be summarized, as well as vital signs and safety assessment of jawline and oral commissures. The results of the urine pregnancy tests will be listed.

All AEs will be monitored by the Sponsor to determine if they meet the criteria of remote spread of effect of the toxin or hypersensitivity. A list of preferred terms for these types of events will be provided in the SAP, and will be further analyzed to determine if there is a plausible possibility that they represent distant spread of toxin or hypersensitivity. In order to perform the analysis, variables including alternative etiology (medical history, concomitant medication, or diagnosis which could account for the symptoms), location of Dysport administration, and temporal relationship to Dysport administration will be considered by the Sponsor.

Effective

Version: 6.0

Effective date: 2019-08-09 13:21

Effective

Version: 6.0

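### SAP 2.5.3 applies one exclusion list to both kinds of AESI candidate, so a hypersensitivity reaction at the injected site can be dropped from the AESI summary by a test that fits only remote toxin spread

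*SAP*

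**What the plan says.** SAP 2.5.3 defines AESIs as "TEAEs that suggest a possible remote spread of effect of the toxin or events suggestive of hypersensitivity like reactions". Each category has its own search. Remote-spread candidates are "identified using the list of MedDRA PTs compatible with the mechanism of action of BoNT-A", also drawing on regulators' recommendations. For the other category, "TEAEs potentially representing hypersensitivity reactions will be identified using the Standardised MedDRA Query (SMQ) (narrow search query) for hypersensitivity reactions".

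The two streams then merge: "All TEAEs identified using the search strategy described above will be medically evaluated" by the sponsor, before database lock and unblinding. One sentence gives the grounds for removal. It opens "Cases will be excluded if they are confounded by presence of alternative clinical etiologies" and continues with three more grounds. The second turns on place, and removes cases "if they are considered to be local effects instead of distant spread as judged by the site of injection". The third turns on onset, and removes a case when "the time period between study treatment administration and event onset is not in accordance with the expected mechanism of action". The fourth is too little information to judge. Only events that the sponsor confirms enter the AESI tables and listings.

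Protocol 9.1.3.1 also pools the two event types but is softer. It lists alternative etiology among the variables to weigh, and says that "location of Dysport administration, and temporal relationship to Dysport administration will be considered by the Sponsor". It does not make any of them an automatic exclusion. SAP 2.1 says that the SAP prevails over the protocol's statistical sections where the two differ.

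**The concern.** Whether an effect is local or distant separates expected toxin action at the injected muscle from spread. It does not separate allergy from non-allergy: a reaction in the injected neck can be local and still be hypersensitivity. The timing ground has a related weakness. It refers to a mechanism of action without saying whose, and the section mentions only the toxin's.

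At stake is the one summary that groups hypersensitivity terms into a single adjudicated figure. The plan treats this risk as distinct: known hypersensitivity to a product component is an exclusion criterion (Protocol 5.2.2), and possible reactions are reported within 24 hours (Protocol 7.2.5.2.2). SAP 2.5.3 describes no AESI table of search-identified events before adjudication, so a reader of the AESI table would not see that cases had been removed, or on which ground.

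**Working it through.** The documents state no AESI rate, count or threshold, so there is no planned figure to reproduce. The check is mainly textual.

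**Step 1. Is any ground limited to one category?** The exclusion sentence has one subject, covering all cases that come out of the two searches. None of its four grounds is restricted to spread candidates, and no separate criteria for hypersensitivity are given.

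**Step 2. Does each ground suit each category?**

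| Ground in SAP 2.5.3 | Suspected remote spread | Suspected hypersensitivity |
|---|---|---|
| Alternative etiology | Applies | Applies |
| Local rather than distant, by injection site | Applies; this is the question being asked | Does not discriminate; a local reaction can be allergic |
| Onset not fitting the mechanism of action | Applies; the mechanism is that of BoNT-A | Unclear; no hypersensitivity timing is stated |
| Insufficient information | Applies | Applies |

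The site ground is therefore misplaced for hypersensitivity on its own wording. The timing ground is ambiguous. The documents give no expected onset window, so the text alone does not establish that any particular onset time would fail.

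**Step 3. Which text governs?** Protocol 9.1.3.1 has location and timing considered; the SAP makes them grounds for removal. Under SAP 2.1 the SAP wording controls.

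**Step 4. Where does an excluded event still appear?** SAP 2.5.2 tabulates all TEAEs and related TEAEs, among others, by treatment group, SOC and PT. SAP 2.1.2 lists all eCRF data. Under SAP 2.6.1 the DSMC reviews the AE list. None of these depends on the AESI adjudication.

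**Step 5. Size per case.** SAP 1.1.2 plans about 60 subjects per dose and up to 60 on placebo. Assume n = 60 in an arm.

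- One case: 1/60 = 1.7 percentage points.
- The documents give no number of such cases, so assume a range of 0 to 3 per arm: 0/60 = 0%, 1/60 = 1.7%, 2/60 = 3.3%, 3/60 = 5.0%.
- Illustration: suppose an arm has two hypersensitivity cases and both are removed. The AESI table then shows 0/60, with exact 95% upper limit 1 − 0.025^(1/60) = 6.0%. With both kept it would show 2/60 = 3.3%, exact (Clopper-Pearson) 95% interval 0.4% to 11.5%.

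These figures show what a lost case is worth. They do not predict that any will be lost.

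**The case against.** The best defense is that the site clause limits itself. Local as opposed to distant spread has meaning only where spread is in question, and the sentence before it names the two review questions separately. A medical reviewer would probably not apply it to an allergy. Likewise, the timing clause does not name the toxin, and for a hypersensitivity candidate it can be read as the timing expected of an allergic reaction. Both readings are sensible, but the SAP states neither. A pre-specified rule should not depend on the reviewer setting part of it aside. This part of the defense lowers the likelihood of harm without removing the defect.

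The limits on the harm do stand. The TEAE tables keep the events by arm, the DSMC sees the AE list, and reporting within 24 hours does not depend on adjudication. Review before unblinding guards against classification by known arm, though not against under-counting. AESI incidence is not named among the safety endpoints in Protocol 2.1.4 or SAP 1.6, and SAP 2.5 plans no inferential safety analysis. What the TEAE tables do not supply is one incidence across the hypersensitivity search terms.

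The defense is also right that site and timing are not worthless for allergy. Protocol 7.2.5.1.7 recognizes injection-related trauma as a procedure effect, and both can help tell the two apart.

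A reader might infer more: that immediate reactions will be excluded, that hypersensitivity incidence is biased toward zero, or that the comparison between arms is lost. The documents do not support these. No onset window is given, the number of affected cases may be zero, and SAP 2.5.2 preserves the comparison by arm at the level of SOC and PT.

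**Conclusion.** The point holds as a defect in a stated rule whose reach is limited. The site ground, followed as written, can remove a hypersensitivity reaction at the injected site from the AESI tables and listings. The timing ground is ambiguous for hypersensitivity and is the weaker part. The result is a risk of under-counting in the adjudicated hypersensitivity incidence, worth about 1.7 percentage points per case on the assumption of 60 subjects in the arm. The overall TEAE reporting and the efficacy analyses are unaffected.

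One limit of the check: the contents of SAP Appendices A and B are not in the text available. The SAP describes them only as term lists, so a category-specific rule there is unlikely but cannot be excluded. The change should be made because the ambiguity is real and cheap to remove.

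**What to change.** In SAP 2.5.3, split the exclusion list by category:

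- **Suspected remote spread:** keep all four grounds, and state that the timing ground refers to the toxin's mechanism of action.
- **Hypersensitivity cases found by the SMQ:** drop the site ground. State that timing is judged for plausibility as a hypersensitivity reaction. Keep the alternative-etiology and insufficient-information grounds.

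It would also help to tabulate, by arm, all events found by each search before adjudication, so that the effect of the exclusions is visible.

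The wording change is a few sentences; the same reviewer reads the same cases and no new data are needed. The additional table is one more output. The downside is small: a few more events, possibly including some injection-procedure effects, may be reported as hypersensitivity AESIs.

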7.2.5.2 Reporting Procedures

7.2.5.2.1 Procedure for Reporting Adverse Events

The collection of AEs is from the time that a subject signs the ICF to their final visit.

At each post-enrollment visit, the Investigator (or sub-Investigator) will question the subject about AEs using an open non-persuasive question to elicit reporting of AEs, for example “Have you noticed any change in your health since the last visit?” Directed questioning and examination will then be performed as appropriate.

Any AE occurring during the AE reporting period, whether it is related to the study product or not, will be recorded immediately in the source document, and described on the AE form of the eCRF along with the date of onset, severity, relationship to the study product, action taken and outcome, without omitting any requested and known information. Additional information may be requested under certain circumstances.

Adverse Events (AEs) assessed as related to the treatment or study procedure will be monitored until they have resolved or reached a stable condition. Other AEs will be monitored until the last visit if they have not resolved or reached a stable condition.

The Investigator will obtain and maintain in the subject’s files all pertinent medical records, information and medical judgment from colleagues who assisted in the treatment and follow-up of the subject. If necessary, the Investigator will contact the subject’s personal physician or hospital staff to obtain further details.

For SAEs (see Section 7.2.5.2.3) and pregnancies (see Section 7.2.5.2.4), the Sponsor is to be informed immediately. The event must be reported by e-mail to the Safety email within 24 hours of receipt of the information (contact details in Section 7.2.5.2.3).

7.2.5.2.2 Procedure for Reporting an Adverse Event that may indicate remote spread of toxin effect or a hypersensitivity reaction

Adverse events that may indicate remote spread of toxin or hypersensitivity reactions (Appendix 6) should be reported to the Safety email [redacted] within 24 hours of awareness using the AE Clarification Form.

Effective date: 2019-08-09 13:21

In case of difficulty to obtain all the required information within 24 hours, an initial report can be submitted with follow up information provided within 24 hours of awareness of the new information.

The following information should be provided on the AE Clarification Form:

- Subject identification (subject number and initials)

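### SAP 2.5.3 drops a flagged event of special interest that cannot be assessed in the same way as one judged unlikely, so the AESI outputs as described can understate possible cases and do not show which is which

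*SAP*

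**What the plan says.** SAP 2.5.3 defines the AESIs as treatment-emergent events that suggest possible remote spread of toxin effect or a hypersensitivity-like reaction. Candidates are found by a term list (Appendix A) and a narrow standard MedDRA query (Appendix B).

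The flagged events are then "medically evaluated during the study, before the database lock and unblinding", and this is done "by the sponsor to identify events which could possibly represent" remote spread or that suggest hypersensitivity due to treatment.

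The section gives four grounds for exclusion:

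- The first reads "Cases will be excluded if they are confounded by presence of alternative clinical etiologies", explained as a history, medication or diagnosis capable of explaining the symptoms.
- The second applies "if they are considered to be local effects instead of distant spread as judged by the site of injection".
- The third is an onset time that does not fit the expected mechanism of action.
- The fourth is "or due to insufficient information/evidence to make an assessment".

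The section closes by fixing what is displayed: "In the tables and listings, only the final list of AESIs confirmed by the sponsor" counts.

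Protocol 7.2.5.2.2 provides follow-up for the same kind of event: "Adverse events that may indicate remote spread of toxin or hypersensitivity reactions (Appendix 6) should be reported to the Safety email" within 24 hours on an AE Clarification Form. Where details are lacking, "an initial report can be submitted with follow up information provided within 24 hours of awareness of the new information".

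**The concern.** The review asks whether an event could possibly be remote spread or hypersensitivity. A case with too little information has not been shown to fall below that threshold; it has not been placed on either side of it. The SAP nevertheless gives it the same result as a case judged unlikely. Missing information is counted as a non-event.

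SAP 2.5.2 treats a missing AE start date differently when deriving onset and duration: the event is assumed to begin on the day of treatment, so it stays in the analysis.

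These are the SAP's named events of special interest in a dose-ranging trial, and the AESI table is where a reader will look for them by dose. A zero there could mean that nothing was flagged, that everything flagged was judged unlikely, or that something flagged could not be judged. The readable text plans no output that tells these apart.

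**Working it through.** The documents give no AESI rate, and no sample size or power statement for AESIs, so there is no figure to reproduce. The check is a comparison of texts, followed by a note on scale.

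**Step 1. What each ground establishes, against a threshold of possible.**

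| Ground in SAP 2.5.3 | What it establishes | Status of the case |
|---|---|---|
| Local effect, judged by injection site | Positive reason to doubt remote spread | Judged unlikely |
| Onset time does not fit the mechanism | Positive reason to doubt the event | Judged unlikely |
| Confounded by an alternative etiology | Another cause is capable of explaining the symptoms | May be unlikely or indeterminate |
| Insufficient information or evidence | Nothing in either direction | Indeterminate |

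The third row matters. A competing explanation is confounding; it does not by itself rule out toxin spread. The indeterminate group is therefore the fourth ground plus some of the cases under the etiology ground.

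**Step 2. Consequence.** All four grounds end in exclusion, and only sponsor-confirmed events enter the AESI tables and listings. The readable SAP text describes no unassessable category, no count of flagged against confirmed events, and no listing of exclusion reasons.

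**Step 3. Where an excluded event can still be seen.**

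- SAP 2.5.2: it stays in the TEAE tables by treatment group, SOC and PT, and in the breakdowns by intensity, causality and seriousness where it qualifies.
- SAP 2.1.2: all eCRF data and derived variables are listed by subject. The sponsor's exclusion reason is not named among them.
- Protocol 7.2.1 and the DSMC section of the SAP: the DSMC reviews the list of AEs. That list includes confirmed spread events but is not restricted to them.

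With the term lists, a reader can find out whether a flagged term occurred in an arm. The reader cannot find out which ground removed it.

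**Step 4. Scale.** SAP 1.1.2 gives about 60 subjects per dose. One subject is 1/60 = 1.7 percentage points. Assume, for illustration only, no confirmed case and 0, 1 or 2 unassessable subjects in one dose arm:

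| Unassessable (assumed) | AESI table shows | Confirmed plus unassessable |
|---|---|---|
| 0 | 0/60 = 0% | 0/60 = 0% |
| 1 | 0/60 = 0% | 1/60 = 1.7% |
| 2 | 0/60 = 0% | 2/60 = 3.3% |

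The AESI table is identical in all three rows. No confidence limits are given: the counts are assumed, and SAP 2.5 plans no inferential analysis of safety endpoints.

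**The case against.** The case for leaving the plan alone has real force.

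- **The confirmed count is already generous.** It admits events that are only possible remote spread. This stands, but it sharpens the point: with so low a bar, an unassessable case has not failed it.
- **Nothing is lost from the study report.** Step 3 of the working bears this out. A reader might infer that excluded events disappear from the safety reporting or are withheld from the DSMC; the documents do not support that. Protocol 7.2.1 describes the DSMC as unblinded, and its AE review is not confined to confirmed events. Whether it is told that a given case was unassessable is not stated in the readable text.
- **The review is blinded.** A reader might infer that the sponsor could remove cases selectively from active arms. The evaluation precedes database lock and unblinding, and nothing in the text points to a differential effect between arms. Under-counting in any arm remains possible.
- **Unassessable cases should be rare.** The Clarification Form collects symptoms, related history, onset, injection details and outcome, which are largely the inputs to the other three grounds. This stands as a limit on size. It does not say how any remaining cases are reported, and the SAP writes a rule for them.
- **Formats are in a companion document** not available here (SAP 2.1.2). This stands as a limit: the point concerns the outputs as the readable SAP describes them. That document supplies formats for outputs the SAP describes, and no output of unassessable cases is described.

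Two further inferences fail. One is that the first three grounds all amount to evidence against the event; the etiology ground does not. The other is that the SAP contradicts Protocol 9.1.3.1, which names etiology, location and timing. That list is worded as open, so a further ground is not a conflict.

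**Conclusion.** The point holds as a low-severity improvement confined to the AESI tables and listings. The rule is complete and readable, and it lets missing information count as a non-event. As described, the AESI outputs can understate possible remote-spread or hypersensitivity cases in any arm, and they do not separate cases judged unlikely from cases left indeterminate.

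The size is probably small: 1.7 points for each unassessable subject in an arm of about 60, with the number of such subjects unknown and expected to be low. The conclusion assumes that the companion document adds no display of exclusion reasons. This is a matter of transparency. It does not threaten the safety conclusion and gives no ground for alleging bias between doses.

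**What to change.** In SAP 2.5.3, keep the sponsor-confirmed AESI count as planned and add the following:

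1. The sponsor records, before unblinding, a disposition and an exclusion reason for every search-flagged TEAE.
2. One table, by dose and pooled placebo and separately for remote spread and hypersensitivity, gives the number of subjects flagged, confirmed, excluded for each reason, and unassessable.
3. Confirmed plus unassessable is shown as a sensitivity count. Cases excluded for an alternative etiology have their own line, so a reader who regards some as indeterminate can see how many there are.
4. One listing gives all flagged events with their disposition and reason.

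The cost is SAP wording, one table, one listing, and one recorded field per flagged case. That field is a small process step, because no passage says the reason is currently captured. The search and the blinded review are already planned. SAP 2.1 lets supportive analyses be added later without an amendment, but a reason reconstructed after unblinding would not be blinded, so the instruction should be in place before the review is finished. The downside is that a less specific count appears beside the confirmed one.
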